Study Protocol

Title: Prevalence of Carotid Web in Youth Assessed by Duplex Sonography: a Cross-Sectional Study

Short Title: Carotid Web in Youth

Acronym: CaWY Study

ID: G25-498516

Version: 1.4

Date: October 20, 2025

Authors: [name] [name], M.D., Ph.D.

[name]., Ph.D.

[name]., Ph.D.

Affiliation: Center for Health Research, Faculty of Medicine, University of Ostrava, Ostrava, Czech Republic

1) Background and Rationale

A carotid web (CaW) is a shelf-like, thin, triangular endoluminal projection—typically arising from the posterior wall of the internal carotid artery (ICA) bulb—considered by many to be an intimal variant of fibromuscular dysplasia and associated with embolic ischemic stroke in otherwise low-risk, younger patients. Although CT angiography (CTA) is most frequently used to diagnose CaW, characteristic appearances are detectable by carotid duplex ultrasound (DUS) on longitudinal B-mode with supportive Doppler findings; microflow/superb microvascular imaging can improve conspicuity. Population prevalence in the general young adult population is unknown; most estimates come from stroke cohorts ($\approx 2\%$ among symptomatic populations; higher within cryptogenic stroke subsets), so a dedicated, population-based sonographic study is needed.

2) Objectives and Hypotheses

Primary objective: Estimate point prevalence of carotid web in a general young adult population aged 15–25 years using duplex sonography.

Secondary objectives:

- Describe CaW laterality and morphology (web thickness, length, and projection angle) on ultrasound.
- Estimate prevalence of concomitant ICA/CCA atherosclerotic change or stenosis.
- Assess inter-observer agreement for CaW detection on DUS.
- In an adjudicated subset, compare DUS-suspected CaW with CTA (optional validation).

Hypothesis: Carotid web is present in 2 % of the general 15–25-year population (two-sided).

(This is a planning assumption; true prevalence may be lower/higher. Literature in symptomatic cohorts ranges roughly 2%, higher in cryptogenic stroke; general-population data are lacking.)

3) Study Design

Cross-sectional, multi-center, population-based sonographic survey with blinded central image adjudication, reported per STROBE guidelines for cross-sectional studies.

4) Study Population

Inclusion criteria

- Age 15 – 25 years at enrollment.
- Able to provide informed consent.

Exclusion criteria (for primary analysis; still recorded if present):

- Prior carotid endarterectomy/stenting, neck irradiation, or known vasculopathy with non-web lesions that preclude assessment.
- Inadequate acoustic window despite optimization (these participants contribute to feasibility metrics, not prevalence numerator/denominator).

Setting & sampling frame

- Community-based recruitment (secondary schools / universities).

- Stratified cluster sampling by sex, age bands (15-17, 18–21, 22–25), and recruitment site to approximate the underlying population.

5) Sample Size

Assumptions

- Expected prevalence $p=0.02$ (2%)
- Desired absolute precision $d=0.01$ ($\pm 1\%$)
- Confidence level 95% $\rightarrow Z=1.96$

Formula

$$n = \frac{Z^2 p(1-p)}{d^2} = \frac{1.96^2 \times 0.02 \times 0.98}{0.01^2} = 752.95$$

$$\frac{1.96^2 \times 0.02 \times 0.98}{0.01^2} = 752.95$$

Required minimum sample size: 753 participants (round up) plus 10% for non-diagnostic/poor-quality scans and no-shows, i.e. **totally 829 participants is needed to screen.**

6) Ultrasound Acquisition Protocol

Equipment & presets

- High-end ultrasound suplex machine Canon Aplio a-series with B-mode, color/power Doppler, spectral Doppler, and microflow/superb microvascular imaging. High-frequency linear transducer PLT-1005BT (5–14 MHz).
- Patient supine, slight neck extension/contralateral head rotation; optimize for the carotid bulb/ICA origin.

Scanning sequence (bilateral)

1. **B-mode:** transverse sweep from distal CCA through bulb into proximal ICA and ECA; then longitudinal (anterolateral, lateral, posterolateral windows).
2. **Color Doppler:** at low PRF to visualize flow separation/recirculation; adjust wall filter and gain to avoid overwriting thin intraluminal structures.
3. **Spectral Doppler:** with angle correction $\leq 60^\circ$, sample volume 1.5–2.0 mm; measure PSV and EDV in standard segments (distal CCA, bulb, proximal ICA).

4. **Microflow imaging:** focused on the posterolateral bulb to delineate thin shelf/membrane and adjacent flow.

Image storage

- Mandatory cine loops (≥ 3 cardiac cycles) in longitudinal and transverse of the bulb/ICA origin, plus still frames with and without color, and spectral Doppler waveforms with angle annotation ((same as in protocol of ANTIQUE study).
- Label side and projection; record machine make/model, probe, presets.

7) Sonographic Definition of Carotid Web

Definite carotid web:

Inclusion criteria:

1. Focal echogenic lesion in carotid bifurcation (15 mm proximally to flow divider and 15 mm distally)
2. The lesion is present (interferes) in the posterior wall
3. Echogenicity of the lesion is higher than intraluminal blood
4. Maximal length of lesions 3.0 mm
5. Minimal intraluminal prominence (width) 2.0 mm
6. In longitudinal view: Shape of lesion is shelf-like nor valve-like, triangular with the sharpest angle proximally with the blood flow direction
7. In transversal view: Transversal linear defect with echogenic surface projecting in the arterial lumen (the shape should be nest-like)
8. Hemodynamic signature: focal flow separation/recirculation or color aliasing immediately distal to the shelf without proportionate atherosclerotic plaque; spectral Doppler may be normal or show subtle focal acceleration without classic stenosis criteria.

Exclusion criteria:

1. The length is greater than the width
2. Visible only in transversal and not longitudinal view
3. Presence of carotid plaque (Mannheim consensus) in the posterior wall

Suspected carotid web:*Inclusion criteria:*

1. Focal echogenic lesion in carotid bifurcation (15 mm proximally to flow divider and 15 mm distally)
2. Minimal intraluminal prominence (width) 1.5 mm
3. One out of these criteria:
 - a. In longitudinal view: Shape of lesion is shelf-like nor valve-like, triangular with the sharpest angle proximally with the blood flow direction
 - b. In transversal view: Transversal linear defect with echogenic surface projecting in the arterial lumen (the shape should be nest-like)

Exclusion criteria:

1. Presence of carotid plaque (Mannheim consensus) in the posterior wall

Differential sonographic features to record: typical plaque (echogenic/heterogeneous with surface calcification), carotid diaphragm, dissection flap (mobile, intramural hematoma), carotid web with superimposed thrombus.

7) Sonographic Case Definition of Carotid Web

Required equipment/settings (if specified in your criteria):

- Probe / frequency: 5-14 MHz
- Settings: MI 1.6, 37 fps, Q scan, dynamic range 70
- Patient position: supine position, slight neck extension/contralateral head rotation

Diagnostic categories (tick all that apply):

- Definite CaW — must meet morphology, location, hemodynamics criteria and exclusions ruled out (plaque, dissection, diaphragm, artifact).
- Probable CaW — meets some morphology criteria and exclusions ruled out (plaque, dissection, diaphragm, artifact).

- Not CaW — meets no criteria for CaW.

Morphologic measurements (standardized):

- Web thickness (mm): ____ (measured at ____)
- Web length/projection into lumen (mm): ____
- Projection angle (°) relative to vessel wall: ____
- Distance from flow divider (mm): ____
- Side: left / right / bilateral

Hemodynamic signatures (as per your thresholds):

- Color Doppler recirculation/aliasing: present / absent (criteria: ____)
- Spectral Doppler acceleration: PSV ____ m/s (cutoff: ____); ICA/CCA ratio cutoff: ____
- Microflow imaging pattern: ____

Differential exclusion checklist (define image features to rule out):

- Atherosclerotic plaque: ____
- Dissection flap/intramural hematoma: ____
- Carotid diaphragm/other membranes: ____
- Artifact (reverberation, blooming): ____

Image acquisition minimums (per side):

- Transverse cine (≥ 3 cycles) focused on bulb/ICA origin
- Longitudinal cine in ≥ 2 insonation planes (lat & post-lat)
- Still frames (B-mode \pm color) with calipers for all measurements
- Spectral Doppler waveforms (CCA, bulb, proximal ICA) with angle correction $\leq 60^\circ$

Quality grading (apply your rules):

- Grade 1 (excellent) / 2 (diagnostic) / 3 (limited) — use only Grades 1–2 in primary analysis; Grade 3 in sensitivity analysis.

Reader guidance & adjudication using your criteria:

- Two blinded readers score Definite/Probable/Possible/Not CaW; discrepancies resolved by third reader under the same rubric.

- 10% repeat reads for κ /ICC.

CRF add-ons (pre-wired to your criteria)

- Checkboxes for each criterion element (present/absent/not evaluable).
- Auto-calculated category (Definite/Probable/Possible/Not CaW) based on boxes ticked.
- Mandatory image IDs linked to each measurement.

8) Training, Blinding, and Adjudication

- Sonographers undergo a standardized training module with exemplar images and checklists.
- **Blinding:** Operators are blinded to participant clinical data except age/sex; central readers (two expert neurosonologists) are blinded to site and each other.
- **Adjudication:** Disagreements (probable/possible/absent) resolved by a third senior reader.
- **Reliability:** 10% random sample re-read for inter-observer agreement (Cohen's κ for categorical calls; ICC for continuous measures).

9) Data Collection

- **Demographics:** age, sex, ethnicity (optional), height/weight.
- **Vascular risk factors:** smoking status, BP at visit, lipid profile if available, personal history of stroke/TIA/migraine, OCP use (females), recreational drugs, connective tissue disease/FMD history.
- **Ultrasound fields:** laterality; CaW category (absent/possible/probable), web dimensions (length, thickness, projection angle—estimate), distance from flow divider, presence of superimposed thrombus, plaque descriptors, standard velocities (CCA, bulb, ICA), ICA/CCA PSV ratio, EDV.
- **Imaging quality scores** and reasons for non-diagnostic studies.

10) Validation Substudy

- Participants with definite or possible CaW on DUS plus 1:2 matched DUS-negative controls (matched by age/sex/site) will invited for CTA within 4 weeks to evaluate concordance (index test: DUS; reference standard: CTA with thin-slice oblique sagittal reconstructions). Outcome: sensitivity/specificity and positive predictive value of DUS criteria. (CTA descriptions of CaW as thin, shelf-like posterior bulb defects guide the reference call.)

11) Outcomes

- **Primary:** Point prevalence of **probable CaW** (participants with ≥ 1 carotid web / all with diagnostic scans), with 95% CI adjusted for sampling design.
- **Secondary:**
 - Prevalence including **possible + probable** (sensitivity analysis).
 - Distribution by side (left/right/bilateral).
 - Association between CaW and sex, smoking, BP, OCP use (exploratory).
 - Inter-observer agreement metrics.
 - In validation substudy: DUS diagnostic accuracy vs CTA.

12) Statistical Analysis Plan

- **Weighting:** Apply sampling weights for cluster/strata to estimate population prevalence; robust SEs (Taylor linearization) or survey-design GLMs.
- **Descriptives:** Means/SDs or medians/IQRs; counts/% with 95% CIs.
- **Primary analysis:** Weighted prevalence and **exact (Clopper–Pearson) or Wilson** CIs for rare events; compare strata with Rao–Scott χ^2 .
- **Regression (exploratory):** Survey-weighted Poisson (log link, robust variance) for prevalence ratios of CaW vs candidate covariates.
- **Reliability:** Cohen’s κ with 95% CI (categorical), ICC(2,1) for continuous measures.
- **Missing data:** Report flow; use complete-case for primary prevalence; multiple imputation for covariate analyses if $>5\%$ missing.

- **Sensitivity analyses:** (i) include **possible** CaW as positive; (ii) restrict to scans with top quality scores; (iii) per-reader estimates.

13) Bias Minimization & Quality Control

- Pre-specified imaging protocol; machine presets harmonized across sites.
- Central training and periodic re-calibration; quarterly site audits of randomly selected studies.
- Consecutive sampling within clusters to reduce selection bias; track response rates.
- Maintain blinding; lock image sets before adjudication.

14) Ethics and Safety

- Minimal-risk imaging study; no ionizing radiation in the primary protocol.
- Informed consent; separate consent for optional CTA.
- Participants with **incidental significant carotid stenosis** or suspected thrombus receive counseling and referral per local care pathways.
- Data privacy per GDPR; coded IDs; secure storage.

15) Feasibility & Timeline

- **July-December 2025:** Finalize SOPs, train sonographers, pilot 50 scans to confirm criteria and quality metrics.
- **January 2026 – June 2026:** Enrollment and scanning.
- **May – June 2026:** Central reads and adjudication.
- **July – December 2026:** Analysis, manuscript preparation.

16) Case Report Forms (CRFs) — Core Fields (summary)

- **CRF-1 (Eligibility & Consent).**
- **CRF-2 (Demographics/Risk).**
- **CRF-3 (Ultrasound Acquisition):** device, probe, settings, windows obtained, quality.

- **CRF-4 (Ultrasound Findings):** CaW category; measurements; Doppler velocities; plaque; stenosis category; images saved (IDs).
- **CRF-5 (Adjudication):** reader A/B calls; consensus; κ .
- **CRF-6 (Validation Substudy):** CTA done (Y/N), CTA result (CaW Y/N), discordance reason.

17) Reporting

- Report per **STROBE**; include gallery of representative DUS images (longitudinal shelf-like lesion, transverse membrane, microflow swirl) and a flow diagram. Explicitly discuss limitations: web detection is operator-dependent; ultrasound criteria are less standardized than CTA; very low prevalence may limit precision without large samples.

Key References (for protocol justification)

1. **Fontaine L, et al.** *Ultrasound characteristics of carotid web*. J Neuroimaging. 2022. Describes B-mode/Doppler appearances; microflow imaging improves detection. ([PMC](#), [PubMed](#))
2. **Chen H, et al.** *Carotid webs: pathophysiology, diagnostic approaches, and management*. J NeuroIntervent Surg. 2024. Overview; ultrasound visualization best in longitudinal B-mode. ([jn.is.bmj.com](#))
3. **Radiopaedia (review).** *Carotid web*. Emphasizes shelf-like defect at posterior ICA bulb and CTA reference standard. ([Radiopaedia](#))

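### Section 5 sizes the study for ±1 point with a simple-random-sample Wald formula, which does not match the planned cluster sample, weights and Clopper–Pearson or Wilson interval

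*Protocol*

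**What the plan says.** Section 5 has three inputs: prevalence 0.02, absolute precision 0.01 and Z = 1.96. It puts them into Z²p(1−p)/d², obtains 752.95 and concludes "Required minimum sample size: 753 participants (round up"). The only inflation is "plus 10% for non-diagnostic/poor-quality scans and no-shows", which brings the number to screen to 829.

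The design and analysis are described elsewhere in the protocol:

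- **Section 4 (Setting & sampling frame):** recruitment through secondary schools and universities, by "Stratified cluster sampling by sex, age bands" and recruitment site.
- **Section 11:** the primary prevalence is to be reported "with 95% CI adjusted for sampling design".
- **Section 12:** sampling weights, Taylor linearization or survey-design models, and Clopper–Pearson or Wilson limits.
- **Section 13:** consecutive sampling within clusters.
- **Section 17:** among the limitations, "web detection is operator-dependent", and a remark that very low prevalence may limit precision.

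The protocol gives no design effect, intra-cluster correlation (ICC), cluster size or number of clusters.

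**The concern.** The Section 5 formula is valid for a simple random sample analysed with a Wald interval. The protocol departs from it in three ways: observations are sampled in clusters, they carry weights, and the interval is not the Wald one. Near 2% the Clopper–Pearson and Wilson limits are asymmetric and somewhat wider than Wald. Clustering and unequal weights can each reduce the effective sample size below the number of scans.

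The study has one primary estimate, and precision is the only justification given for its size. Someone reading Section 5 would expect roughly 1.0% to 3.0% if 2% is observed. The planned analysis will give a wider interval that reaches further upward. The reported result is not biased by this; what is at stake is whether the stated planning precision is true of the study as designed.

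**Working it through.** **Inputs.** From Section 5: p = 0.02, d = 0.01, Z = 1.96, n = 753, 829 to screen. From Section 12: Clopper–Pearson or Wilson. The design effect (DEFF) is not in the document and is assumed below.

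**1. The protocol's own figure.** 1.96² × 0.02 × 0.98 / 0.01² = 752.95, rounded up to 753. This reproduces exactly, and the Wald half-width at n = 753 is 1.00 point. For the number to screen, 753 × 1.10 = 828.3, rounded up to 829.

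**2. Planned intervals, no clustering and equal weights.** At an observed 2% (0.02 × 753 = 15.06 positives, used as a fractional count):

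- Wilson: centre (p + z²/2n)/(1 + z²/n), half-width z√(p(1−p)/n + z²/4n²)/(1 + z²/n). Result 1.22% to 3.27%, half-width 1.03 points.
- Clopper–Pearson (beta quantiles): 1.13% to 3.27%, half-width (3.27 − 1.13)/2 = 1.07 points.
- Upper arm in both: 3.27 − 2.00 = 1.27 points.

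Averaged over binomial variation at a true 2%, the expected half-width is 1.02 (Wilson) or 1.07 (Clopper–Pearson). It is 1 point or less in about 46% and 26% of samples respectively.

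**3. Scans needed for a 1-point half-width, still with no clustering.** 792 (Wilson) or 861 (Clopper–Pearson). For an upper arm of at most 1 point: 1118 or 1124.

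**4. Does the 10% allowance cover the gap?** If 10% are lost as planned, 829 × 0.90 = 746 scans remain, fewer than 753. Wilson reaches 792 only if losses stay below 1 − 792/829 = 4.5%. Clopper–Pearson needs 861, which exceeds 829 even with no losses.

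**5. Effect of an assumed design effect.** Effective n = 753/DEFF, observed prevalence 2%; half-widths (hw) in percentage points:

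| DEFF (assumed) | Effective n | Wald hw | Wilson 95% CI (hw) | Clopper–Pearson 95% CI (hw) | Scans needed by the protocol's formula (752.95 × DEFF) |
|---|---|---|---|---|---|
| 1.0 | 753 | 1.00 | 1.22–3.27% (1.03) | 1.13–3.27% (1.07) | 753 |
| 1.2 | 627.5 | 1.10 | 1.16–3.42% (1.13) | 1.06–3.43% (1.19) | 904 |
| 1.5 | 502 | 1.22 | 1.09–3.64% (1.27) | 0.96–3.64% (1.34) | 1130 |
| 2.0 | 376.5 | 1.41 | 1.00–3.97% (1.49) | 0.84–3.98% (1.57) | 1506 |

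For orientation, DEFF = 1 + (m − 1) × ICC. With an assumed cluster size m = 20 and ICC = 0.01 this is 1 + 19 × 0.01 = 1.19; with m = 30 and ICC = 0.02 it is 1 + 29 × 0.02 = 1.58. Unequal weights are not included.

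**6. Could stratification rescue the figure?** DEFF would have to be at most 753/792 = 0.95 (Wilson) or 753/861 = 0.87 (Clopper–Pearson). The protocol claims no such gain.

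**The case against.** The strongest reply is that the certain part is small. Half-widths of 1.03 and 1.07 are close to a target that Section 5 calls only desired, and asymmetry is normal for a valid interval near 2%. That stands, and it limits the severity.

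Second, anything larger depends on a design effect the document does not give. That also stands. A reader might infer that the interval must be far wider than ±1 point, for instance from m = 40 and ICC = 0.05, where DEFF = 1 + 39 × 0.05 = 2.95. The document does not support this. At p = 0.02 an ICC of 0.05 implies a between-cluster standard deviation of √(0.05 × 0.02 × 0.98) = 3.1 points, more than the mean prevalence itself. Even an ICC of 0.01 implies 1.4 points.

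Third, a reader might infer from the operator-dependence remark in Section 17 that positives will cluster by site or sonographer. They may, but the protocol does not establish it. Section 8 plans standardized training and two central readers blinded to site, with a third to adjudicate. Section 13 adds harmonized presets and re-calibration. What remains is mainly variation in image acquisition, since readers can judge only what was captured. Section 4 also names recruitment site among the stratifiers. If site is a stratum, between-site differences do not inflate the stratified variance. The text leaves open whether site is stratum or cluster.

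Fourth, Section 2 admits that prevalence may be lower or higher than 2%. At 1% and DEFF 1.5 all three half-widths are below 1 point (Wald 0.87, Wilson 0.94, Clopper–Pearson 0.99). This is true, but the stated precision is for 2%. The Section 17 caveat concerns low prevalence and does not correct Section 5.

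Finally, the sample-size justification is stated in the protocol, so a separate analysis plan would not make that statement right.

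**Conclusion.** The point holds as a mismatch between the sample-size formula and the planned design and analysis; it is not an arithmetic error. Under the planned interval methods, at an observed 2% and with no clustering or weighting loss, ±1 point is missed by 0.03 (Wilson) to 0.07 (Clopper–Pearson) points of half-width, with an upper arm of +1.27. This part needs no assumption from outside the document.

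Further widening from clustering and unequal weights is possible but of unknown size. The figures for design effects of 1.2 to 2.0 are illustrations, not predictions.

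A reader might also infer that the reported interval will understate uncertainty or that the study is too small to be useful. Neither follows: Sections 11 and 12 already plan a design-adjusted interval, and no test or decision rule depends on reaching ±1 point. The protocol should be corrected, but this is a should-fix matter and does not undermine the study.

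**What to change.** Keep 829 to screen. In Section 5:

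- Replace the ±1% claim by the expected 95% interval at 2% under the planned interval method, for design effects from 1.0 to 2.0. With Clopper–Pearson this runs from 1.13–3.27% at 1.0 to 0.84–3.98% at 2.0.
- Label the design effects as assumed, and give the cluster size and ICC behind them.
- State that 753 is the effective sample size that gives ±1 point with a Wald interval, not the number of scans that guarantees it under this design.

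This is a rewording of one section and adds no participants. Its only cost is a less favourable stated precision.

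### Minor: 829 is 753 × 1.10, so if 10% of those screened are lost it leaves about 746 diagnostic scans, 7 below the stated minimum of 753

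*Protocol*

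**What the plan says.** Section 5 (Sample Size) of the Protocol uses the precision formula for a single proportion, with an expected prevalence of 2%, an absolute precision of ±1 percentage point and 95% confidence. The result, 752.95, becomes "Required minimum sample size: 753 participants (round up"). The same sentence continues "plus 10% for non-diagnostic/poor-quality scans and no-shows" and ends with "totally 829 participants is needed to screen".

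Three other places fix what counts towards the primary estimate:

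- Section 4 (Study Population), on inadequate acoustic windows: "these participants contribute to feasibility metrics, not prevalence numerator/denominator".
- The quality grading under Sonographic Case Definition of Carotid Web (the second section numbered 7): "use only Grades 1–2 in primary analysis; Grade 3 in sensitivity analysis".
- Section 11 (Outcomes) defines the denominator of the primary prevalence as participants with diagnostic scans, and Section 12 makes the primary prevalence a complete-case analysis.

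**The concern.** The 753 comes from a formula for the number of participants who contribute to the prevalence estimate. Given the exclusions in Sections 4, 7 and 11, it must therefore be the number left once unusable scans and absentees are gone.

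An allowance for such losses is normally a proportion of the people one sets out to screen, because that is the group in which the losses arise. To end with n after losing a proportion L of those screened, one divides n by (1 − L). Multiplying n by (1 + L) always gives a slightly smaller number. Section 5 multiplies. Under the natural reading of its own allowance, the recruitment target is then a little below what its own minimum requires.

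What is at stake is the consistency of one sentence and a trivial amount of precision. The 753 has no slack, since it comes from rounding 752.95 up, so any shortfall takes the planned half-width just above the stated 1 percentage point.

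**Working it through.** **Inputs, all from Section 5:** p = 0.02; d = 0.01; Z = 1.96; allowance 10%; number to screen 829.

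**1. The minimum, reproduced.** n = Z²p(1 − p)/d² = 1.96² × 0.02 × 0.98 / 0.01² = 752.95, rounded up to 753. This agrees with the Protocol.

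**2. The number to screen, reproduced.** 753 × 1.10 = 828.3, rounded up to 829. This agrees with the Protocol. Division gives a different figure: 753/0.90 = 836.7, rounded up to 837. So 829 was obtained by adding 10% of 753.

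**3. What 829 yields at several loss rates among those screened.** The rates other than 10% are shown for range and are not in the Protocol.

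| Loss among the 829 | Expected diagnostic scans | Against 753 |
|---|---|---|
| 8% | 829 × 0.92 = 762.7 | above |
| 9% | 829 × 0.91 = 754.4 | above |
| 10% | 829 × 0.90 = 746.1 | 7 below |

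The break-even loss is (829 − 753)/829 = 76/829 = 9.17%.

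**4. Effect on precision.** The half-width is 1.96 × √(0.02 × 0.98/n), the same simple-random-sample Wald form that underlies the Protocol's formula.

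- n = 753: 1.000 percentage points
- n = 746: 1.005 percentage points

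**5. The alternative figure.** 837 × 0.90 = 753.3, which meets 753 in expectation. The difference from 829 is 8 participants, or 8/829 = 1.0%.

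**6. Expectation is not a guarantee.** If each person screened is lost independently with probability 0.10, the number retained from 837 has a standard deviation of √(837 × 0.90 × 0.10) = 8.7. The chance of retaining at least 753 is then about 54% with 837 screened and about 23% with 829. The 7-scan shortfall is less than one standard deviation.

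**The case against.** The strongest reply is that the sentence is correct as written. It says 753 plus 10%, and 753 plus a tenth of 753 is 829 after rounding. The Protocol nowhere states that 10% of those screened will be lost. This stands: a reader might infer that Section 5 contains a miscalculation, or that 829 will leave 746 scans as a matter of fact, and the documents support neither. The figure of 746 depends on reading the 10% as a loss rate among those screened. What the reply leaves open is that, taken literally, the margin covers 9.2% and the Protocol does not say so.

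A second reply is that people who do not turn up are never scanned. If the 829 are those who attend, part of the 10% falls outside them, the loss among the 829 is below 10%, and 746 is too low. This is possible. However, the Protocol puts absentees and unusable scans into one allowance on the way to the number to screen, so counting both within the 829 is the more natural reading.

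A third reply is that the effect is negligible. This stands in full. A half-width of 1.005 still rounds to the target, and the 10% is a round figure without a stated source, so 9.2% and 10% are hardly distinguishable as forecasts. A reader might infer that the primary analysis will miss its precision goal in a way that matters. The documents do not support that either. This is an estimation study in which no test or stopping rule depends on reaching 753, and 829 is worded as a number needed, not as a cap. The interval to be reported is also a weighted, design-adjusted Clopper–Pearson or Wilson interval (Sections 11 and 12), so the 0.005-point change does not describe it.

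**Conclusion.** The point holds in conditional form and is minor. If the 10% is the expected loss among those to be screened, 829 is 8 short of the 837 that division gives, and it leaves about 746 diagnostic scans in expectation, 7 below the minimum stated in the same sentence. The corresponding half-width is 1.005 instead of 1.000 percentage points, computed as a Wald interval under simple random sampling with a prevalence of 2%.

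The conclusion rests on two assumptions: that 753 is the number required in the primary denominator, which Sections 4, 7 and 11 make clear, and that the allowance is a proportion of those screened, which is natural but unstated. The study's conclusions are not threatened.

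**What to change.** Restate the figure in Section 5 and say what the 10% refers to. Either of two wordings would do:

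- Keep 829, and state that it gives 753 diagnostic scans only if losses from unusable scans and no-shows together are at most 9.2% of those screened, with about 746 expected at 10% loss.
- Give 753/0.90 = 837 as the number to screen at an assumed 10% loss, and describe it as meeting 753 in expectation, not as a guarantee.

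The first costs one clause and changes no recruitment. The second costs one number and 8 further participants. Neither alters the design or the analysis.

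### The two Section 7 texts set different exclusions for the lower carotid-web tier: the Suspected rule, applied alone, can admit mimics that the Probable rule rejects

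*Protocol*

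**What the plan says.** **First Section 7 (Sonographic Definition).** Definite carotid web carries a wall requirement: "The lesion is present (interferes) in the posterior wall". Its exclusions are a lesion longer than it is wide, a lesion seen only in transverse view, and posterior-wall plaque.

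Suspected carotid web has three inclusion criteria:
- a location, "Focal echogenic lesion in carotid bifurcation (15 mm proximally to flow divider and 15 mm distally"), with no wall named;
- a size, "Minimal intraluminal prominence (width) 1.5 mm";
- a shape, "One out of these criteria", either the longitudinal or the transverse appearance.

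Its only exclusion is "Presence of carotid plaque (Mannheim consensus) in the posterior wall". After both tiers comes a list headed "Differential sonographic features to record: typical plaque (echogenic/heterogeneous with surface calcification), carotid diaphragm, dissection flap" and further items. These are to be recorded; nothing there says that they disqualify a lesion.

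**Second Section 7 (Sonographic Case Definition).** The lower tier is called Probable: the lesion "meets some morphology criteria and exclusions ruled out (plaque, dissection, diaphragm, artifact"). A differential checklist further down names the same four mimics as things to rule out, with the image features left blank.

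**Labels elsewhere.** The readers and the CRF's auto-calculated category use Definite, Probable, Possible and Not. Section 10 invites definite or possible cases to CTA. Section 11 makes probable carotid web the primary outcome and possible plus probable a secondary one. Suspected is not a category in any of these. Section 2 speaks of DUS-suspected webs when describing the CTA comparison, but does not tie the term to a tier.

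**The concern.** The Suspected tier widens the inclusion to any wall but keeps a plaque exclusion written for a posterior-wall lesion. It also drops the Definite exclusion of lesions seen only in transverse view, so a transverse linear defect alone satisfies the shape test. A membrane or flap could plausibly enter that way.

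The second Section 7 would exclude such a lesion. The same scan can therefore be a case under one text and not under the other. The CRF derives the category automatically from ticked boxes, so one rule has to be programmed, and the protocol does not say which. At stake is an upward bias in whichever prevalence the Suspected tier feeds. A confidence interval does not show a bias of this kind.

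**Working it through.** **Step 1. The two texts side by side.**

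| Item | First Section 7, Definite | First Section 7, Suspected | Second Section 7, Probable |
|---|---|---|---|
| Wall | posterior required | none named | none named |
| Minimum prominence | 2.0 mm | 1.5 mm | not stated |
| Shape | longitudinal and transverse | either one | some morphology criteria |
| Plaque excluded | posterior wall | posterior wall | any wall |
| Diaphragm, dissection | record only | record only | must be ruled out |
| Artifact | not mentioned | not mentioned | must be ruled out |

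The conflict lies in the last three rows. The missing wall requirement departs from the Definite list, not from the Probable text, which names no wall either. The diaphragm, dissection and artifact gap is shared by the first text's Definite list, although the second text requires the same four exclusions for Definite too. What is peculiar to Suspected is the mismatch between an any-wall inclusion and a posterior-only plaque exclusion.

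**Step 2. What passes the first text alone.** A lesion on a non-posterior wall, within 15 mm of the flow divider, with prominence of at least 1.5 mm and one shape feature, qualifies even if it is plaque, provided there is no posterior-wall plaque. A diaphragm or flap meeting the same size and shape tests also qualifies. The second text rejects all of these.

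**Step 3. Where it lands.**
- Suspected = Probable: it enters the primary outcome (Section 11). As Section 10 is written, probable cases are not invited to CTA, so the substudy is not the route.
- Suspected = Possible: it enters the possible-plus-probable estimate (Sections 11 and 12) and the CTA substudy (Section 10), where false cases lower the positive predictive value. The primary outcome is not affected. The conflict is then with the differential checklist, since the second Section 7 never defines Possible.

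**Step 4. Scale.** Inputs from Section 5: p = 0.02, d = 0.01, Z = 1.96.
- Plan's own figure: 1.96² × 0.02 × 0.98 / 0.01² = 752.95, rounded up to 753; 753 × 1.10 = 828.3, rounded up to 829. Both reproduce.
- Expected cases: 0.02 × 753 = 15.06, about 15.
- One false case: 1/753 = 0.13 percentage points.
- False cases needed to match the planned ±1 point: 0.01 × 753 = 7.5, so 8 exceed it (8/753 = 1.06 points).

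The protocol gives no rate of mimics. The table below assumes false-positive rates f among web-free participants, a true prevalence of 2% and perfect sensitivity. False cases = 753 × 0.98 × f; apparent prevalence = 0.02 + 0.98f; true share = 0.02/(0.02 + 0.98f).

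| Assumed f | False cases | Apparent prevalence | True share |
|---|---|---|---|
| 0.25% | 1.8 | 2.2% | 89% |
| 0.5% | 3.7 | 2.5% | 80% |
| 1% | 7.4 | 3.0% | 67% |
| 2% | 14.8 | 4.0% | 51% |

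These rows show sensitivity to an unknown. They do not estimate it.

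**The case against.** The strongest reply is that the two lists are compatible. A narrower and a broader exclusion can be applied together, and the result is the broader one. The harm arises only if the first text is used alone, which no section directs, and the reader rubric and CRF use the second text's vocabulary. This stands as far as it goes. A reader might infer that the lists cannot both be applied, and the documents do not support that. But no section says that they are cumulative or which one governs the programmed category.

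There are also safeguards. Two blinded expert readers and a third adjudicator make the calls, and plaque descriptors are collected, so plaque-bearing cases could be found afterwards. This lessens the risk but does not remove it: adjudication applies whatever rubric it is given, and no reclassification rule is stated.

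It is also fair to say that plaque should be scarce at ages 15 to 25. The protocol gives no figure for that, just as it gives none for a high mimic rate, and it makes concomitant atherosclerotic change a secondary objective. Neither side can claim a size.

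Finally, much of the problem stems from the unmapped labels. That is true, but mapping the labels alone would still leave two exclusion lists for the tier.

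**Conclusion.** The point holds as an inconsistency between two definitions of the lower tier. Read on its own, the first Section 7 can count mimics that the second excludes, and the direction of the resulting bias is upward. This rests on two conditions: the first text is applied alone, and the mimic meets the 1.5 mm and shape criteria. The size is unknown beyond 0.13 percentage points per false case at n = 753.

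Three stronger readings should be avoided:
- A reader might infer that the primary prevalence and the CTA predictive value are both compromised. They belong to different label mappings, and the protocol does not state which mapping applies.
- A reader might infer that accepting any wall contradicts the second Section 7. It does not, because that text sets no wall for Probable.
- A reader might infer a bias larger than the planned precision. That takes about eight false cases, and nothing in the protocol says how many to expect.

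The matter is worth correcting before images are read. It does not invalidate the design.

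**What to change.** Reconcile the two Section 7 texts before central reads, which Section 15 places in May to June 2026:

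1. State that the exclusions already in the second Section 7 (plaque without wall limit, dissection, diaphragm, artifact) apply to every positive tier, including Suspected. Keep the existing Definite exclusions. An exclusion limited to plaque at the lesion's own site would be narrower than both current texts, so it should not replace them.
2. Map Suspected to one reader and CRF label, and use that label in Sections 7 to 12.
3. Program the auto-calculated CRF category from that single list.

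The exact image criteria, including the blank checklist entries, are for the investigators to settle. The cost is wording and CRF logic, and possibly a slightly smaller count in the lower tier. No change to the sample size or scanning protocol follows from this point.
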